Care in the perioperative period will otherwise be standardized. In the post-anesthesia care unit (PACU), hydromorphone or morphine will be titrated by the PACU nurse for the subject's comfort. Additionally, as standard of care, Physical Therapy will evaluate patients in the PACU before discharge.

An outline of study time points and assessments is shown in **Table 2**.

Table 1. Post-Op Follow Up Assessment Schedule

Post-Op Day	Time of Text Message	Data Collection Time Period
POD 0	Right before discharge	Waking up from surgery to discharge
POD 1-AM	9:00 AM	Discharge to 11:59 midnight prior
POD 1-PM	3:00 PM	12:00 AM midnight night prior to 12:00 PM noon same day
POD 2-AM	9:00 AM	12:01 PM noon day prior to 11:59 PM midnight night prior
POD 2-PM	3:00 PM	12:00 AM midnight prior to 12:00 PM noon same day
POD 3-AM	9:00 AM	12:01 PM noon day prior to 11:59 PM midnight night prior
POD 3-PM	3:00 PM	12:00 AM midnight prior to 12:00 PM noon same day

Table 2. Summary of Study Procedures and Follow-Ups	
Study Activities	Details/Assessments
Informed consent	
 Obtain informed consent
Baseline	
 Pre-Operative VAS Pain Score Quad Strength Pre-Op HOOS Jr PROMIS-10 Global Health
Randomization (day 0)	
 Confirm eligibility criteria Randomization
Randomization procedure (day 0)	
 Complete PENG or QL Block according to randomization allocation
Post-Op First Opportunity in PACU	
 Opioid Consumption
Ambulation (Assessed by Physical Therapy in PACU)	
 Time that first ambulation occurred in PACU Distance ambulated in PACU Quad Strength in PACU
Post-Op Day 1 9:00 AM (text message)	
 Opioid and pain medication consumption VAS Pain Score
Post-Op Day 1 3:00 PM (text message)	
 Opioid and pain medication consumption VAS Pain Score
Post-Op Day 2 9:00 AM(text message)	
 Opioid and pain medication consumption VAS Pain Score
Post-Op Day 2 3:00 PM (text message)	
 Opioid and pain medication consumption VAS Pain Score
Post-Op Day 3 9:00 AM (text message)	
 Opioid and pain medication consumption VAS Pain Score

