Post-Op Day 3 3:00 PM (text message)	
 Opioid and pain medication consumption VAS Pain Score Satisfaction with analgesia Side Effects of nausea/vomiting, itching, over sedation, respiratory concerns related to opioids Adverse Events
Day 7 Post-Op 9:00 AM (text message)	
 HOOS JR PROMIS-10 Global Adverse Events
Week 2-3 Post-Op (scheduled SOC clinic visit or telephone)	
 HOOS JR PROMIS-10 Global Adverse Events
Week 6 Post-Op (scheduled SOSC clinic visit or telephone)	
 HOOS JR PROMIS-10 Global Averse Events
After completion of 6-week post-op follow-up	
 All study activities complete

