11.0 Data Management

- **Sample size and power:** The primary outcome for assessing differences between PENG+LFC vs. QL blocks will be postoperative cumulative opioid consumption (in IV morphine mg equivalents; IV MME) over time, up to 72 hours postoperatively. Cumulative opioid consumption will be evaluated in PACU, and at 12-hour intervals during the first 72 hours of the postoperative window. Differences in cumulative opioid consumption over time between block groups will be assessed using a linear mixed model approach. The model will include fixed effects for treatment group, postoperative time, and the interaction between block group and postoperative time and a random subject effect to account for correlation between measures collected on the same patient over time. Differences between block types at each postoperative time will be evaluated using linear contrasts from the model. A previous study⁹ conducted at MUSC found mean IV MME at 12 hours postop in subjects undergoing THA with a QL block was 16 ± 12 MME. A sample size of 48 subjects per group with 9 repeated measures of opioid consumption provides 80% power to detect a difference in cumulative MMEs consumed postoperatively of 4 MMEs at significance level $\alpha = 0.006$ (Bonferroni adjusted for 9 pairwise comparisons between group) assuming a standard deviation of ± 12 MMEs, a first-order autoregressive correlation structure and correlation between observations on the same subject of $\rho = 0.33$. We will plan to enroll 53 subjects/group (106 total) to allow for 10% attrition.
- Postoperative VAS pain score captured in the preoperative area, PACU and 12-hour intervals during the first 72 hours of the postoperative window will be collected as a secondary outcome and will be evaluated using a LMM similar to the primary outcome. Additional outcomes of interest include time to first ambulation, functional and mobility outcomes, PACU duration, patient satisfaction, and opioid related side effects.

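### The power calculation uses 9 repeated opioid measures and 9 comparisons, but the protocol schedules 7; with 7 the stated 80% falls to about 70% at the adjusted alpha, and the powered test is not named

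*Combined protocol and SAP*

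**What the plan says.** Section 11.0 defines the primary outcome as cumulative opioid consumption up to 72 hours and gives the measurement times: "Cumulative opioid consumption will be evaluated in PACU, and at 12-hour intervals during the first 72 hours of the postoperative window". The analysis is a linear mixed model with group, time, their interaction and a random subject effect. The tests it describes are per-time contrasts: "Differences between block types at each postoperative time will be evaluated using linear contrasts from the model".

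The power statement in the same section starts from "A sample size of 48 subjects per group with 9 repeated measures of opioid consumption" and claims "80% power to detect a difference in cumulative MMEs consumed postoperatively of 4 MMEs". The alpha is 0.006, explained as "Bonferroni adjusted for 9 pairwise comparisons between group". The other inputs are an SD of 12 MME, first-order autoregressive correlation with ρ = 0.33, and 53 enrolled per group to allow for 10% attrition.

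Section 10.0 holds the schedule. The table headed "Table 1. Post-Op Follow Up Assessment Schedule" has one POD 0 row, then an AM and a PM row on each of POD 1, 2 and 3. Table 2 lists opioid consumption from "Post-Op First Opportunity in PACU" through six text messages, the last at "Post-Op Day 3 3:00 PM". Its day 7, week 2–3 and week 6 rows list no opioid data.

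**The concern.** The number of repeated measures affects this calculation twice: it sets the precision of an average over time, and it is the divisor for alpha. If 9 is wrong, the stated power of the primary outcome is wrong too, unless another reading of the test rescues it.

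The power sentence also does not say which hypothesis it refers to. The Bonferroni wording points to the contrasts at individual times, so the 80% is easily read as the power of those contrasts. Under the same inputs the power differs greatly between a time-averaged difference and a single-time contrast, so a reader cannot tell what the trial is able to detect.

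**Working it through.** **Counting the assessments**

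| Source | Count |
|---|---|
| Section 11.0, schedule: PACU + 12, 24, 36, 48, 60, 72 h | 1 + 6 = 7 |
| Section 10.0, Table 1: POD 0 + (AM, PM) × 3 days | 1 + 6 = 7 |
| Section 10.0, Table 2: PACU + six text messages | 1 + 6 = 7 |
| Section 11.0, power statement | 9 |

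The VAS schedule adds a preoperative score and still reaches only 8. Nothing in the document supplies two further opioid assessments.

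**Inputs** (all Section 11.0): n = 48 per group, SD = 12, difference = 4 MME, AR(1) with ρ = 0.33, alpha = 0.006. Sidedness is not stated; two-sided is assumed.

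**Formulas**

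- Variance factor for the mean of m AR(1) measures: F = (1/m²) ΣΣ ρ^|i−j|. This gives F = 0.2024 for m = 9 and F = 0.2536 for m = 7. For a single time, F = 1.
- Standard error of the group difference: SE = 12 × √(2F/48).
- Power ≈ Φ(4/SE − z), with z the two-sided critical value: 2.748 at 0.006, 2.773 at 0.05/9, 2.690 at 0.05/7, 1.960 at 0.05. The opposite tail is negligible.

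**Reproducing the plan's figure (time-averaged, m = 9)**

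SE = 12 × √(2 × 0.2024/48) = 1.102, and 4/1.102 = 3.630.

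- At 0.006: Φ(3.630 − 2.748) = 81.1% (79.1% with a t reference on 94 df).
- At 0.05/9: Φ(3.630 − 2.773) = 80.4%.

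This matches the stated 80%. Alternatives at 0.006 with 9 measures do not: one-sided gives 86.8%, and exchangeable correlation at 0.33 gives 42.9%. A single-time contrast, which does not depend on the number of measures, gives about 13%. So the test behind the 80% appears to be a two-sided time-averaged difference with 9 measures, but this is inferred.

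**Same test with the scheduled 7 measures**

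SE = 12 × √(2 × 0.2536/48) = 1.234, and 4/1.234 = 3.243.

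| Alpha | Power, n = 48 | Difference for 80% power |
|---|---|---|
| 0.006 | 69.0% | 4.43 MME |
| 0.05/7 | 71.0% | 4.36 MME |
| 0.05 (one test) | 90.0% | 3.46 MME |

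With the t reference the three powers are 66.6%, 68.8% and 89.4%. At 0.05/7, 80% power needs 56.9, so 57 evaluable per group, more than the 53 to be enrolled. If all 53 per group are evaluable, power is 74.5% at 0.006 and 76.3% at 0.05/7.

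**Contrast at one postoperative time**

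SE = 12 × √(2/48) = 2.449, and 4/2.449 = 1.633.

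- At 0.006: Φ(1.633 − 2.748) = 13.2%; 80% power needs 8.79 MME.
- At 0.05/7: Φ(1.633 − 2.690) = 14.5%; 80% power needs 8.65 MME.

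**Type I error**

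7 × 0.006 = 0.042, so with 7 contrasts the stated alpha is mildly conservative. If 9 contrasts were really intended, 9 × 0.006 = 0.054, a small excess because 0.05/9 = 0.00556 was rounded up.

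**The case against.** The mismatch between 9 and 7 cannot be explained away. The strongest reply concerns what follows from it.

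- **The shortfall depends on an inferred test.** A single time-averaged contrast needs no Bonferroni split, and at 0.05 it would have 90.0% power with 7 measures. This is correct, but the plan states alpha 0.006 and names no such contrast. At the stated alpha, neither the time-averaged nor the single-time reading reaches 80% with 7 measures.
- **The recalculated figures use AR(1), while the planned model has a random subject effect**, which on its own implies exchangeable correlation. With exchangeable correlation at 0.33 and 7 measures, power is 42.6% at 0.05/7 and 70.6% at 0.05. This stands as a caution: the figures here show the effect of the count under the plan's stated power assumptions, and the restated power should use the correlation structure that will be fitted.
- **An SD of 12 comes from one time (12 hours) and is applied to a cumulative outcome up to 72 hours.** This also stands. The single-time figures hold only under that flat SD.
- **The low single-time power is not caused by the count.** True: changing 9 to 7 moves it by only a point or two. It arises because the powered test is unnamed, which is a separate part of the same defect.
- **Consequences are limited.** With 7 contrasts the false-positive rate is not raised. Section 13.0 keeps data up to withdrawal, so the effective n lies between 48 and 53, which puts time-averaged power at 0.05/7 between 71% and 76%.

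**Conclusion.** The concern holds. The power statement uses 9 measures and 9 comparisons where the protocol schedules 7, and the stated 80% depends on the 9. On the plan's own inputs (48 per group, SD 12, AR(1) with ρ = 0.33, 4 MME, two-sided), correcting the count takes the time-averaged test from about 80% to 69–71% at the Bonferroni alpha. The per-time contrasts that the plan actually describes have 13–15% power for 4 MME. Only a single time-averaged test at 0.05, which the plan does not specify, would exceed 80%. The results assume two-sided testing and the plan's SD and correlation at every time. This should be fixed: it is an inconsistency in the primary outcome's power statement, and with 7 contrasts it carries no type I error inflation.

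**What to change.** 1. In Section 11.0, change both counts from 9 to 7. If 9 was intended, define the two further opioid assessments, bring Tables 1 and 2 into line, and use an alpha that does not exceed 0.05/9 (0.0055, not 0.006).
2. With 7, set the per-contrast alpha to 0.05/7 = 0.0071, stated as 0.007 (7 × 0.007 = 0.049).
3. Name the test to which the power refers, state its sidedness, and give the power for that test under the correlation structure of the fitted model. Under the plan's present inputs with 48 per group, the figures would be:
   - about 71% for a 4 MME time-averaged difference at 0.05/7;
   - about 90% if that difference is one test at 0.05;
   - about 15% for 4 MME at a single time, where 80% power corresponds to about 8.7 MME.

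The cost is wording and a recalculation. Endpoint, model, schedule and the enrolment of 106 can stay as they are. Unless a single time-averaged test at 0.05 is chosen, the sponsor accepts and discloses a less favourable figure. Restoring 80% for the time-averaged test at 0.05/7 would instead take 57 evaluable per group, or 57/0.9 = 63.3, so 64 enrolled per group (128 in total).

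### The 80% power for a 4 MME difference belongs to a time-averaged comparison; the Bonferroni-adjusted contrasts actually planned at each time have about 13%

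*Combined protocol and SAP*

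**What the plan says.** Section 11.0 (Data Management, sample size and power) takes cumulative opioid consumption in IV MME, up to 72 hours, as the primary outcome. It is to be analysed with a linear mixed model containing block group, postoperative time, their interaction and a random subject effect. The between-group tests are then described: "Differences between block types at each postoperative time will be evaluated using linear contrasts from the model".

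The sample size statement reads "A sample size of 48 subjects per group with 9 repeated measures of opioid consumption" and continues that this "provides 80% power to detect a difference in cumulative MMEs consumed postoperatively of 4 MMEs at significance level" 0.006, explained as "Bonferroni adjusted for 9 pairwise comparisons between group". The assumptions are given as "assuming a standard deviation of ± 12 MMEs, a first-order autoregressive correlation structure", with a within-subject correlation of 0.33. The SD comes from an earlier study at the same institution, which "found mean IV MME at 12 hours postop in subjects undergoing THA with a QL block was 16 ± 12 MME".

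The section does not say that the 4 MME is an average over time, and it names no time-averaged test. Section 4.0 also defines the outcome only as cumulative consumption over time.

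**The concern.** Dividing alpha by nine makes sense only if nine separate between-group tests are run, one per time. A number of repeated measures and a within-subject correlation affect power only if the test pools information across times. The power statement uses both: it pays the multiplicity penalty of per-time tests and takes the precision of a pooled test.

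This is the trial's only sample size justification. If the 80% does not apply to the planned contrasts, a null result would be read as evidence against a 4 MME benefit from a trial described as powered to find it, when the trial had little chance of finding it at any one time. Ethics reviewers and readers would also be misinformed about what the trial can detect.

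**Working it through.** **Inputs, all from Section 11.0.** Difference 4 MME; SD 12 MME; 48 evaluable per group; nine measures; AR(1) with correlation 0.33; alpha 0.006 (0.05/9 = 0.00556, rounded up). Sidedness is not stated, so two-sided is assumed. The critical value is z(0.997) = 2.748, and z(0.80) = 0.842.

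**1. Reproducing the 80%: difference averaged over nine measures.**
- Variance factor for the mean of nine AR(1) measures: the sum of 0.33^|i−j| over all pairs, divided by 81, = 16.395/81 = 0.2024.
- Effective SD = 12 × √0.2024 = 5.40.
- SE of the group difference = 5.40 × √(2/48) = 1.102.
- 4/1.102 = 3.630; power = Φ(3.630 − 2.748) = 81.1% (79.1% with the noncentral t).
- At alpha 0.05/9 the power is 80.4% and the required n is 48 per group, the plan's own number.

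This is evidently the calculation behind the statement.

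**2. The planned test: contrast at one time.** With time as a categorical factor and complete data, the contrast at one time is the difference between two group means at that time. The other eight measures do not reduce its variance, and the correlation does not enter.
- SE = 12 × √(2/48) = 2.449.
- 4/2.449 = 1.633; power = Φ(1.633 − 2.748) = 13.2% (12.6% with the noncentral t).
- Detectable difference at 80% power = (2.748 + 0.842) × 2.449 = 8.8 MME, which is 55% of the 16 MME reference mean (8.8/16).
- Sample size for 4 MME at 80% power = 2 × (12/4)² × (2.748 + 0.842)² = 232 per group.

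**3. Other readings of the claim.**

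| Reading | Power for 4 MME |
|---|---|
| One time, one-sided 0.006 | 19.0% |
| One time, all 53 per group | 15.1% |
| One time, two-sided 0.05 with no adjustment | 37.2% |
| At least one of nine contrasts significant, 4 MME at every time (simulation, 400,000 draws) | about 65% |
| Same, for seven times | about 57% |

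For 80% power at one time, the SD would have to be 4/(3.589 × √(2/48)) ≈ 5.5 MME, less than half the assumed 12.

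**4. How firm the time-averaged figure is.** It needs nine measures and a low correlation. Section 11.0 and Table 1 schedule seven times (PACU plus six 12-hour periods). With seven measures, power at alpha 0.006 falls to 69.0%. With nine measures it falls to 38.2% at a correlation of 0.7 and to 19.4% at 0.9. As one test at two-sided 0.05 and correlation 0.33, it would be 95% with nine measures and 90% with seven; at correlation 0.7 these become 69% and 62%.

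**The case against.** The strongest reply is that nothing was miscalculated: the stated inputs do give about 80%, and the model contains a group effect through which differences over time are assessed, so an overall comparison may have been intended. The first part is right; the fault is a mismatch between test and power, not a wrong sum. The second part helps little. No overall test is named, one overall test would need no division of alpha by nine, and if it was intended then the stated alpha is the part that does not fit.

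A second reply is that the 13% assumes categorical time, which the plan does not state. If time were linear, contrasts at single times would borrow strength. Under the plan's other assumptions their SEs run from 1.88 MME at the ends to 1.09 in the middle, and power from about 27% to 82%. That reading sits badly with contrasts at each time, and it still does not give 80% at every time.

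A third reply is that the SD of 12 was observed at 12 hours only. A cumulative total may well vary less in the PACU and more by 72 hours. With the difference held at 4 MME, per-time power is about 70% at an SD of 6 and about 6% at an SD of 16. This stands as a limit on quoting one figure for all times, but the constant SD is the plan's own assumption.

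**Conclusion.** The concern holds. The stated power and the planned tests do not belong together. Under the plan's own SD, sample size and alpha, with time categorical and the test two-sided, a contrast at one time has about 13% power for 4 MME, not 80%, so a true difference of that size at a given time would be missed about 87% of the time. The trial has 80% power at one time only for about 8.8 MME. The per-time result does not depend on the assumed correlation; it does depend on SD 12 applying at that time. No reading examined brings the nine contrasts as a set to 80%.

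**What to change.** Make the power statement in Section 11.0 match the test that decides the trial. There are two ways to do so.

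1. **Keep the per-time contrasts as the primary tests.** State that 48 per group gives 80% power for about 8.8 MME at a single time, and about 13% for 4 MME, at alpha 0.006 with SD 12. Say that time is categorical, give the sidedness, note that the SD was observed at 12 hours, and align the number of comparisons with the scheduled times. The cost is wording and a less favourable detectable difference.

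2. **Name the time-averaged group difference as the single primary test** at two-sided 0.05, and make the per-time contrasts supportive with their multiplicity adjustment. Recompute power for the seven scheduled measures, and justify the correlation: 0.33 gives 90%, but 0.7 gives 62%, and successive cumulative totals are likely to be strongly correlated. This is a substantive amendment and must be made before unblinding.

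Neither requires additional patients. The first is sufficient to correct the statement; the second is a design choice for the sponsor.

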4.0 Study Endpoints

- The primary outcome will be postoperative cumulative opioid consumption (in IV morphine mg equivalents: IV MME) over time, up to 72 hours postoperatively. Cumulative opioid consumption will be evaluated at in PACU, and through 72 hours post-op.
- Secondary outcomes: Postoperative pain score measures on the visual analog scale (VAS) captured in the preoperative area, PACU, and through 72-hours post-op.
- Additional outcomes of interest include time to first ambulation, functional and mobility outcomes, PACU duration, patient satisfaction, and opioid related side effects.

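### The per-time contrasts of cumulative opioid use rest on plain Bonferroni, which is valid but inefficient; a step-down procedure would find more, provided the covariance is corrected with it

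*Combined protocol and SAP*

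**What the plan says.** Section 4.0 defines the primary outcome as "postoperative cumulative opioid consumption (in IV morphine mg equivalents: IV MME) over time, up to 72 hours postoperatively". Section 11.0 fits a linear mixed model with group, time, their interaction and a random subject effect, and then states: "Differences between block types at each postoperative time will be evaluated using linear contrasts from the model". No single primary time is named.

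The adjustment appears only in the sample-size sentence of Section 11.0. There, 48 patients in each arm, measured 9 times, are said to give 80% power for a "difference in cumulative MMEs consumed postoperatively of 4 MMEs". The per-comparison alpha is 0.006, explained as "Bonferroni adjusted for 9 pairwise comparisons between group". The spread is given by "assuming a standard deviation of ± 12 MMEs". For the dependence, the sentence names "a first-order autoregressive correlation structure and correlation between observations on the same subject of" a stated value, 0.33. The analysis sentences themselves name no multiplicity method.

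The times described in Section 11.0 (PACU, then every 12 hours to 72 hours) number 1 + 6 = 7, not 9. The present point holds for either count, so both are shown below.

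**The concern.** The totals are nested: the 24-hour total contains the 12-hour total, and so on. Contrasts at successive times therefore share data and tend to be strongly correlated. Bonferroni uses none of this, and it keeps every contrast at the first-step threshold even after others have been rejected. Holm rejects everything that Bonferroni at 0.05/m rejects and can reject more, under any dependence. A step-down max-|t| procedure also lowers the first-step threshold when the correlation is high. Both hold familywise error at 5% if the test statistics are valid. What is at stake is how many times can be declared different in a trial whose individual contrasts already have little power.

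**Working it through.** **Inputs from Section 11.0.** 48 per group; difference 4 MME; SD 12 at every time; 9 measures; AR(1) with correlation 0.33; alpha 0.006 (0.05/9 = 0.00556, rounded up). Sidedness is not stated, so two-sided is assumed.

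**1. The plan's own figure.** The variance of the mean of 9 AR(1) measures is 12² × f, where f = [9 + 2 Σ(9 − k)0.33^k]/81 = 0.2024 (k = 1 to 8). Then n = 2 × 144 × f × (z + 0.842)²/4².
- At alpha 0.05/9 (z = 2.773): 18 × 0.2024 × 3.615² = 47.6, so 48 per group. The stated size reproduces, but for a difference averaged over time.
- For a contrast at one time, f = 1. At alpha 0.006 (z = 2.748), n = 18 × 3.590² = 232 per group. With 48 per group the noncentrality is 4/(12 × √(2/48)) = 1.63 and the power about 13%.

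**2. Familywise error with correct variances.** The correlation of the 12-hour increments is not in the documents, so a range is assumed: independent, AR(1) 0.33 and exchangeable 0.33, with equal increment variances. Independent increments give correlation √(j/k) between totals j < k, hence 0.71 or more between neighbours. Simulating the largest |t| over the contrasts (94 df), with each contrast tested at 0.006:

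| Dependence | 7 times | 9 times |
|---|---|---|
| Running totals, independent to exchangeable 0.33 increments | about 2.4% down to 1.7% | about 2.7% down to 1.9% |
| The plan's AR(1) 0.33 applied to the measures themselves | not the plan's case | about 5% |

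Separate runs differ by about 0.1 to 0.2 percentage points. For running totals the 5% max-|t| cutoff is 2.39–2.53 with 7 times, against 2.75 for Bonferroni at 0.05/7. With 9 times it is 2.42–2.58, against 2.84 at 0.05/9. Under the plan's AR(1) 0.33 with 9 measures the max-|t| per-test alpha is about 0.0058, so there is no first-step gain.

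**3. Familywise error under the planned model.** A random subject effect alone implies one variance at all times, whereas the variance of a running total grows. With independent equal increments the variance at time k is proportional to k. Over 9 times the average is 5 and the last is 9, a ratio of 1.8. A nominal cutoff of 2.748 then acts as 2.748/√1.8 = 2.05 at the last time, a type I error of about 4% instead of 0.6%. Across the three increment assumptions the last-time error is about 4–7%. Familywise error is 4.8–6.8% with 7 times and 5.5–7.6% with 9.

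**4. Gain from stepping down, like for like.** Mean number of significant contrasts, Bonferroni at 0.05/m against Holm, with correct variances and the same noncentrality at every time:

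| Times | Noncentrality | Bonferroni | Holm |
|---|---|---|---|
| 7 | 2.5 | 2.8 | about 3.5 |
| 9 | 2.5 | 3.4 | about 4.1 |
| 7 | 1.63 (plan's effect) | 0.96 | about 1.2 |
| 7 | 1.63, AR(1) 0.33 on the measures | 0.96 | about 1.1 |

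The chance of at least one significant contrast is unchanged, because Holm's first step is Bonferroni. At noncentrality 1.63 with 7 totals and independent increments it is 33.2% both ways. Step-down max-|t| gains more: for 9 running totals at the plan's effect, average per-contrast power rises from about 13% to 22–26% (normal approximation).

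**The case against.** The strongest reply is that Bonferroni is valid, that Section 11.0 makes no false statement here, and that preferring another method is not a finding of error. That stands, and the point is offered only as an efficiency gain.

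A reader might infer more, and four such inferences are not supported.

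- **That the primary tests run at about half the intended error.** This needs an assumed correlation between increments and correct variances. The only correlation the documents state, AR(1) 0.33, gives about 5% with 9 measures. One may doubt that AR(1) 0.33 with a constant SD fits nested totals, but then the planned random-subject model is in doubt too, and with it the error may exceed 5%.
- **That the adjustment can be swapped on its own.** Stepping down loosens thresholds. Applied to pooled-variance contrasts that may already be too liberal at late times, it would make matters worse.
- **That the gain is free.** It depends on a credible covariance, and it separates tests from intervals.
- **That the 7-time gain should be read against the 0.006 cutoff of 2.81.** That mixes in the mismatch between 7 and 9. The fair comparator for 7 times is 2.75.

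It is also fair to say that the Bonferroni alpha sits in a planning sentence. No rule for the final tests is declared, and the same edit would fill that gap.

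**Conclusion.** A cheap improvement, not a defect in error control. Given valid variances, a step-down procedure keeps 5% familywise control and every rejection that Bonferroni at 0.05/m would make, and it adds some. Because 9 × 0.006 = 0.054, a p-value between 0.00556 and 0.006 is not covered by that guarantee.

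The part due to stepping down needs no correlation assumption. It is modest at the plan's effect (about 0.1 to 0.3 more significant contrasts of 7) and larger at noncentrality 2.5 (about 0.7 more of 7). The part due to nested dependence rests on the assumed increments and vanishes under the plan's stated correlation. Everything is conditional on changing the pooled-variance structure. None of it cures the low per-contrast power, which arises because 48 per group suits a time-averaged difference while the tests are made time by time.

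**What to change.** In the analysis text of Section 11.0, state that the group contrasts over the scheduled times will be tested at familywise 0.05 by Holm, or by step-down max-|t|, using variances (and for max-|t| the joint covariance) from an unstructured or robust covariance. Fix the number of scheduled times in the same sentence, and say whether the rule also covers the VAS model. Settle this before unblinding.

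Holm is the simpler choice because it needs no correlation assumption. Step-down max-|t| gains more where the totals are strongly correlated.

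The text change is small, but there are costs:
- The max-|t| cutoff depends on the estimated correlation and cannot be printed in advance.
- Single-step simultaneous intervals may include zero for a contrast that step-down testing rejects; the plan should say so.
- An unstructured covariance has 7 × 8/2 = 28 parameters at 7 times, or 9 × 10/2 = 45 at 9, with about 96 evaluable patients. A robust covariance is the alternative if that fit is unstable.

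No extra patients or data are needed.

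### The stated 80% power for a 4 MME difference depends on AR(1) correlation 0.33 and a constant SD of 12, which do not fit the planned model or a running-total outcome

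*Combined protocol and SAP*

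**What the plan says.** All of this stands in section 11.0 (Data Management, sample size and power). The primary outcome is cumulative IV MME, evaluated in PACU and then every 12 hours to 72 hours. It is analysed in a linear mixed model with group, time and their interaction, and "a random subject effect to account for correlation between measures collected on the same patient over time". Groups are compared at each time by linear contrasts. No residual correlation structure is named for this model.

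The power statement opens with "A sample size of 48 subjects per group with 9 repeated measures of opioid consumption provides 80% power". The target difference is 4 MME on the cumulative scale, tested at alpha 0.006, which the section describes as "Bonferroni adjusted for 9 pairwise comparisons between group". The variability input is given as "assuming a standard deviation of ± 12 MMEs". The correlation input is "a first-order autoregressive correlation structure and correlation between observations on the same subject of" 0.33. The SD comes from an earlier study at the same institution, where "mean IV MME at 12 hours postop in subjects undergoing THA with a QL block was 16 ± 12 MME". No source is given for the 0.33.

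**The concern.** Three inputs look mismatched.

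- **Structure.** A random subject effect with nothing added gives one common correlation between any two times. The power calculation instead lets the correlation decay, to 0.33^8 = 0.0001 between the first and last of 9 measures.
- **Nesting.** Each cumulative total contains all earlier ones. Unless later use is negatively related to earlier use, adjacent totals are strongly correlated and their SD grows.
- **Timing of the SD.** A 12-hour SD is carried unchanged to 72 hours.

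The sample size draws its strength from averaging weakly correlated measures. If that gain is not real, readers of a null result would credit the trial with a sensitivity to 4 MME that it does not have.

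**Working it through.** **Inputs from section 11.0:** n = 48 per group, difference 4, SD 12, alpha 0.006, 9 measures, rho 0.33. **Assumption:** a two-sided test (sidedness is not stated), so z = 2.748.

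**Formulas.** For the group difference averaged over m measures, D is the mean of all entries of the m × m correlation matrix.

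- SE = 12 × √D × √(2/48)
- Power ≈ Φ(4/SE − 2.748)
- Difference detectable with 80% power = (2.748 + 0.842) × SE

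**Step 1: reproduce the plan's figure.** For AR(1) with rho 0.33 and m = 9, D = 0.202, SE = 1.10 and power is 81% (79% by noncentral t). The mean pairwise correlation under this structure is only 0.10. Other readings do not reproduce 80%: a contrast at a single time gives 13%, and a one-sided averaged test gives 87%.

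**Step 2: vary only the correlation.** SD 12, a constant difference of 4 and 9 measures are kept.

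| Correlation of the totals | D | SE | Power | Detectable difference (MME) |
|---|---|---|---|---|
| AR(1) 0.33 (stated) | 0.202 | 1.10 | 81% | 4.0 |
| AR(1) 0.5 | 0.284 | 1.31 | 62% | 4.7 |
| AR(1) 0.7 | 0.445 | 1.63 | 38% | 5.9 |
| Exchangeable 0.33: (1 + 8 × 0.33)/9 | 0.404 | 1.56 | 43% | 5.6 |
| Exchangeable 0.6 | 0.644 | 1.97 | 24% | 7.1 |
| Exchangeable 0.8 | 0.822 | 2.22 | 17% | 8.0 |
| Independent equal increments, corr √(j/k) for j < k | 0.719 | 2.08 | 21% | 7.5 |
| Contrast at one time (any correlation) | 1 | 2.45 | 13% | 8.8 |

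The values 0.6 to 0.8 for exchangeable correlation and 0.5 to 0.7 for AR(1) are assumed ranges, not figures from the documents.

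**Step 3: what 0.33 means for a running total.** Take two adjacent totals, each with SD 12 and correlation 0.33.

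- Variance of the use between them: 2 × 144 × (1 − 0.33) = 193, SD 13.9.
- Covariance of that use with the total so far: 144 × (0.33 − 1) = −96.5.
- Correlation: −96.5/(12 × 13.9) = −0.58.

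Heavy early users would have to become markedly light users. By contrast, independent increments of equal variance give adjacent correlations of 0.71 to 0.94 over 9 totals.

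**Step 4: the SD over time.** If 12-hour increments are independent with SD 12 each, the SD at 72 hours is 12 × √6 = 29.4. The average of the six 12-hourly totals then has SD 19.1 and SE 19.1 × √(2/48) = 3.89. Power for that average depends on how the group difference evolves, which the plan does not say:

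| Group difference over time | Mean difference (MME) | Power |
|---|---|---|
| Fixed at 4 throughout | 4.0 | 4% |
| Grows by 4 per 12 h, stops at 24 h | 7.3 | 19% |
| Grows by 4 per 12 h, stops at 36 h | 10.0 | 43% |
| Grows by 4 per 12 h to 72 h | 14.0 | 80% |

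**The case against.** The strongest reply is that the arithmetic is right on its stated inputs, so the dispute is about assumptions, and that the averaged test examined here is not one the plan names. Both statements are true. With complete data, the planned contrast at each time does not depend on the within-subject correlation at all. That does not help the claim, because this contrast has 13% power for 4 MME at SD 12. The averaged test matters because it is the reading under which 80% appears.

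Several stronger readings are tempting, and the documents do not support them:

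- *That the plan fixes an exchangeable structure.* This is inferred from silence about residuals. AR(1) residuals could be added to the mixed model, and power depends on the true correlation of the data, not on the label of the fitted model. The structural mismatch shows that the section is not reconciled with itself; the nesting of the totals carries the loss of power.
- *That running totals cannot be so weakly correlated.* Negatively related or very unequal increments, such as a small PACU total before a larger one, could lower the correlation. Implausibly weak is as far as one can go.
- *That power is at most 43%.* This is one scenario, not a bound. AR(1) with rho 0.5 gives 62%, and exchangeable 0.33 with all 53 per group retained gives 48%. Exchangeable 0.33 at constant SD also carries the implausible −0.58 of step 3.
- *That power is really about 4%.* That result lets the SD grow while holding the difference at 4. A difference in cumulative use may also accumulate, so 4% is one end of a range reaching 80%.

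**Conclusion.** Wrong as written. The 80% holds for a difference averaged over 9 measures under AR(1) 0.33 and constant SD 12, and those inputs fit neither the natural reading of the planned model nor a cumulative outcome.

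For the stated constant difference of 4 MME, with 48 per group, SD 12 and two-sided alpha 0.006, the alternatives in step 2 give 17% to 62% for the averaged test and 13% for the planned contrast at each time. The corresponding detectable differences run from 4.7 to 8.0 MME and 8.8 MME. None of these alternatives restores 80%. The only route back to 80% in the working is a difference that keeps growing to 24 MME (6 × 4) at 72 hours, which is a different claim from 4 MME.

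The true figure cannot be fixed from the documents, because they give neither the SD after 12 hours nor any observed correlation between totals.

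**What to change.** In section 11.0, replace the AR(1) 0.33 and constant SD 12 inputs with the SD at each time and the correlations of cumulative MME from the earlier study that supplied the 12-hour figure. If these are unavailable, show a stated range of correlations and of SD growth, with an explicit time profile for the group difference. State the residual structure of the mixed model. Name the test to which the power refers, and restate its power or detectable difference at 48 per group.

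The cost is a re-run of the calculation and a less favourable stated figure. No change in enrolment is needed.
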